The purpose of this plan is to give a complete and detailed description of the statistical analyses and the descriptive statistics that will be included in the report for the study REDOX. This SAP is based on protocol version “200122 REDOX Final Study Protocol v1.8_FINAL” The study biostatistician at Uppsala Clinical Research Center (UCR) is responsible for the writing of the plan and the execution of the statistical analyses. The results will be presented according to the output specification (see Appendix 2 Output Shells). This plan is completed prior to un-blinding/closing of the study database. The study report will include the analyses of the primary endpoint and secondary objectives concerning the primary endpoint. Following secondary objectives will not be analyzed and reported at UCR:

Compared to patients with LTOT prescribed for 15 h/day, does continuous oxygen therapy 24 h/day:

- Fail to reduce the rate of an incident diagnosis of cardiovascular disease?
- Fail to reduce the level of breathlessness?
- Fail to reduce fatigue?
- Fail to improve level of self-reported physical activity?
- Fail to improve health-related quality of life (HRQOL)?
- Fail to improve cognition?
- Fail to increase the patient’s preference in continuing LTOT?

The statistical methods for the above are described in this plan, in order to be outlined before the analysis database is un-blinded and locked. However, these will be analyzed subsequently by the Sponsor Region Blekinge.

2 SAP version history

Version	Date	Reason for change
1.1	2023-04-05	
1.2	2023-04-06	See previous version
1.3	2023-04-24	See previous version

3 Abbreviations and definitions

Different patient groups will be used in the tabulations. The group *All randomized patients* consists of all patients who have fulfilled all the inclusion criteria but not any of the exclusion criteria, submitted signed informed consent to participate in the study and thereby received a patient number (=randomization number). Incorrectly registered patients are not included.

Screened subject	Patients who has signed the Informed Consent Form (ICF)
Randomized subjects	Patients who have fulfilled eligibility criteria and have been randomized
Screening failure	Patients that have been screened but have not been randomized, will be considered as screen failures
Withdrawals	Patients that were randomized but did not complete the study
Discontinued	Patients who discontinued LTOT

Summary table of abbreviations and definitions used in this plan

AE	Adverse event
COPD	Chronic obstructive pulmonary disease
DV	Derived variables
EVF	Erythrocyte volume fraction
FEV ₁	Forced expired volume in one second
VC	Vital capacity
ITT	Intention-to-treat – all randomized patients who has started LTOT, regardless of adherence (see section 6.1 in this SAP)
IQR	The InterQuartile Range (the second and third quartiles, or the middle half of the data set)
kPa	Kilopascal
LPO	Last patient out
LTOT	Long-term oxygen therapy
OS	Output shells
PaO ₂	Partial pressure of arterial oxygen
PP	Per protocol – patients who fulfill certain criteria (see section 6.2 in this SAP)

R-RCT	Registry-based, randomized, controlled trial
SAE	Serious adverse event
Safety population	All randomized patients who have started LTOT. This includes incorrectly randomized patients.
SAP	Statistical analysis plan
SD	Standard deviation
SUSAR	Suspected unexpected serious adverse reaction
Swedevox	Swedish register for respiratory failure
UCR	Uppsala Clinical Research centre

4 Study objectives and outcome variables

4.1 Objectives

Long-term oxygen therapy (LTOT) prescribed 24 h/day vs. 15 h/day. Centers prescribing LTOT in the Swedish quality register for respiratory failure (Swedevox). Study end is defined as Last Patient Out (LPO), which is the date when last patient has been followed for 12 months.

4.1.1 Primary objective

Compared to patients with LTOT prescribed for 15 h/day, does continuous oxygen therapy 24 h/day fail to reduce the rate of all-cause death or first hospitalization at one year?

4.1.2 Secondary objectives

Compared to patients with LTOT prescribed for 15 h/day, does continuous oxygen therapy 24 h/day: (underlined objectives will be analyzed and reported by UCR)

- Fail to reduce the mortality rate from all causes?
- Fail to reduce hospitalization rate from all causes?
- Fail to reduce mortality rate from respiratory disease?
- Fail to reduce mortality rate from cardiovascular disease?
- Fail to reduce hospitalization rate from respiratory disease?
- Fail to reduce hospitalization rate from cardiovascular disease?
- Fail to reduce the rate of an incident diagnosis of cardiovascular disease?
- Fail to reduce the level of breathlessness?
- Fail to reduce fatigue?
- Fail to improve level of self-reported physical activity?
- Fail to improve health-related quality of life (HRQOL)?
- Fail to improve cognition?
- Fail to increase the self-reported oxygen utilization?
- Fail to decrease the rate of LTOT withdrawal?
- Fail to increase the patient's preference in continuing LTOT?

4.2 Outcome variables

The outcome variables that will be analyzed and reported at UCR are underlined. This will be performed in the subgroups stated in Section 6.4. The secondary outcome variables that are not underlined will be analyzed later by the sponsor Region Blekinge with methods outlined in this SAP.

4.2.1 Primary outcome variable

All-cause mortality or 1st hospitalization 1 year after randomization.

4.2.2 Secondary outcome variables

- Mortality rate from all causes at 3 and 12 months
- Mortality rate from respiratory disease at 3 and 12 months
- Mortality rate from cardiovascular disease at 3 and 12 months
- Hospitalization rate from all causes at 3 and 12 months
- Hospitalization rate with a primary diagnosis of respiratory disease or respiratory infection at 3 and 12 months
- Hospitalization rate with a primary diagnosis of cardiovascular disease at 3 and 12 months
- Rate of an incident diagnosis of cardiovascular disease at 3 and 12 months

Self-reported questionnaire data collected at 3 and 12 months:

- Self-rated oxygen utilization
- Breathlessness (Multidimensional Dyspnea Profile; MDP)
- Fatigue (FACIT-Fatigue)
- Informant-rated cognition (IQCODE and FAQ)
- Self-rated cognition (BAS)
- Health-related quality of life (CAT and EQ5D-5L)
- Global impression of change from baseline (GIC)
- Self-reported physical activity
- Preference of continuing treatment

5 Study design

5.1 Design

This is a multicenter, single-blinded (analyst), effectiveness, phase IV, register-based, randomized controlled trial (R-RCT).

5.2 Population

Inclusion Criteria

- Age 18 years or older
- Standard eligibility criteria for non-palliative LTOT at rest (see protocol for references):

- $\text{PaO}_2 < 7.4 \text{ kPa}$ or oxygen saturation $< 88\%$ breathing air, *or*
- $\text{PaO}_2 < 8.0 \text{ kPa}$ on air and either signs of heart failure or polycythemia ($\text{EVF} > 0.54$)

Exclusion Criteria

- Standard contraindications for LTOT
 - Smoking or contact with open fire
 - Other inability to safely comply with LTOT
- Already on LTOT for more than 4 weeks
- Inability to comply with any of the study interventions (LTOT 15h /day or 24 h/ day) as judged by the responsible oxygen staff
- Opt out from being registered in Swedevox
- Inability to give informed written consent to participate in the study as judged by the responsible oxygen staff
- Lack of Swedish identification number
- Previous participation in the study

5.3 Interventions

Intervention: LTOT prescribed for 24 h/day.

Control: LTOT prescribed for 15 h/day. The patient is instructed to use LTOT during sleep and to not use LTOT for a total 9 hours during daytime.

Treatment duration: From the date of randomization to 12 months after randomization (end of trial).

5.4 Follow-up

5.4.1 Clinical follow-up

The patient's medical record will be marked with the allocated LTOT duration at each center, to facilitate follow-up of the prescribed LTOT duration at subsequent clinical contacts. Clinical contacts, other treatments, and follow-up are undertaken according to routine clinical care at each center and are unaffected by study participation. Adverse events are reported within the framework of the routine clinical care.

5.4.2 Registry-based follow-up

All 48 units prescribing and managing LTOT in Sweden report to the National Registry for Respiratory Failure (Swedevox). Data on patient characteristics and the prescribed oxygen therapy are obtained from Swedevox. The completeness of the baseline data will be checked using Swedevox and optimized through contacts with participating centers by the national Swedevox coordinator and by the Study Coordinator.

The main endpoints of mortality and hospitalizations are assessed using national Swedish governmental registries: date and causes of death (Causes of Death Register), and the date and diagnoses/procedural codes of hospitalizations (National Patient Register of in- and outpatient care). Data are cross-linked

between registers using each participant's unique Swedish identity number. In addition, data will be obtained on dispensed outpatient medications (Prescribed Drug Register). Endpoints are assessed at 3 and 12 months after randomization (study end).

5.4.3 Questionnaire and reminder at 3 and 12 months

At 3 months (range 2 to 5 months) and 12 months (range 10 to 14 months) after randomization, all non-deceased participants (according to the Population Register) are sent a letter marked by the patients randomization number by the UCR Registry Unit (separated from the Clinical Research Unit responsible for managing of the study) which includes: 1) a standardized reminder about the allocated treatment to the patient and caregiver(s) (see study protocol, Appendix 2); 2) a questionnaire including data on smoking and on secondary endpoints (see study protocol, Appendix 3) and instructions about how to fill out and return it within 2 weeks in a stamped return envelope. If the questionnaire has not been returned to the UCR data management unit within 3 weeks, a reminder letter is sent home to the patient. The questionnaire data are entered into a database as reported (missing and incomplete data accepted) and quality checked by the UCR data management unit.

5.5 Blinding

This is a single-blinded (analyst) trial. The coordinating investigator, UCR study staff and statistician responsible for analyzing the study data will be blinded to the allocated treatment group. The patient, principal investigators and co-investigators, responsible study nurses, study monitor, caregiver, and the clinical oxygen staff will be aware of the allocated daily treatment duration.

5.6 Study outline

- Patient starting LTOT
- Inclusion/exclusion criteria
- Written consent
- Randomization in Swedevox at or within four weeks of starting LTOT
- Questionnaire three months after randomization, including self-reported adherence
- Study end at 1 year after randomization:
 - Primary endpoint of all-cause mortality or hospitalization
 - Secondary endpoints (registries and 12-month questionnaire, including self-reported adherence)

5.7 Study assessments

Item	Baseline	3 months	1 year (study end)
Swedevox Register			
Demographics	X		
Height and weight	X		
Spirometry	X		
Blood gases on air and oxygen	X		
Primary and secondary causes of starting LTOT	X		
Oxygen dose, equipment and duration	X		
Use of long-term mechanical ventilator	X		X
Date and reason of LTOT withdrawal		X	X
Causes of Death Register			
Date, place, and causes of death		X	X
Patient Register			
Diagnoses / comorbidity and procedures	X	X	X
Hospitalizations	X	X	X
Prescribed Drug Register			
Dispensed drug prescriptions	X	X	X
Clinical visits			
Adverse events		(X) ^a	(X) ^a
Patient questionnaire			
Self-reported oxygen utilization		X	X
Breathlessness (MDP; NRS of worst; refractory; mMRC)		X	X
Fatigue (FACT-Fatigue)		X	X
Self-reported physical activity (modified Grimby questionnaire)		X	X
Cognitive questionnaires (BAS, IQCODE and FAQ)		X	X
HRQOL (EQ5D-5L and CAT)		X	X
Global impression of change (GIC)		X	X
Treatment preference		X	X

^aAdverse events will be collected at the patient's ordinary clinical visits.

6 Definition of analysis populations

As non-adherence to the allocated treatment might cause a potential bias towards equivalence between treatments, in which analysis according to the intention to treat (ITT) principle would not be conservative, all endpoints will be analyzed according to both the ITT and the Per Protocol (PP) principle in the subpopulations stated in section 6.3.

The classification of study patients into different analysis populations will be performed after the unblinding of treatment allocation to the analyst.

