6.1 Intention to treat (ITT) population

A randomized patient will only be excluded from the analysis ITT set if LTOT was never started.

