6.3 Safety population

All randomized patients who have started treatment with long-term oxygen therapy (LTOT) belong to the *Safety population* and will be studied with regard to adverse events. If there are no incorrectly randomized patients or patients who started the wrong treatment, the safety population will be the same as the ITT population.

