6.4 Subpopulations

Primary analysis:

- I. All randomized participants

Secondary analyses:

- II. Participants with more severe resting hypoxemia ($\text{PaO}_2 < 7.4 \text{ kPa}$ on air) at LTOT start
- III. Participants with more moderate hypoxemia ($\text{PaO}_2 7.4\text{--}8.0 \text{ kPa}$ on air) at LTOT start
- IV. Participants with verified COPD (COPD as primary diagnosis and $\text{FEV}_1/\text{FVC} < 0.7$ after bronchodilation) [defined using primary diagnosis + spirometry in Swedevox]
- V. Participants with primary diagnosis other than COPD

7 Statistical analysis

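### The verified-COPD and non-COPD subgroups are defined inconsistently and can overlap, ITT membership of incorrectly randomized patients is ambiguous, and sets that need no allocation are assigned after unblinding

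*SAP*

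**What the plan says.** **Timing.** Section 6: "The classification of study patients into different analysis populations will be performed after the unblinding of treatment allocation to the analyst". No set is excepted. Section 5.5 says that the coordinating investigator, "UCR study staff and statistician responsible for analyzing the study data will be blinded to the allocated treatment group"; patients, site investigators and oxygen staff know the allocation.

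**ITT and safety.** Section 6.1: "A randomized patient will only be excluded from the analysis ITT set if LTOT was never started". The ITT entries in section 3 and in the derived variables agree. Section 3 defines the safety population by the same two conditions, randomized and LTOT started, and adds: "This includes incorrectly randomized patients". Section 6.3 and the footnote to output-shell Table 1 then say: "If there are no incorrectly randomized patients or patients who started the wrong treatment, the safety population will be the same as the ITT population". Elsewhere in section 3, randomized subjects are "Patients who have fulfilled eligibility criteria and have been randomized", and the group of all randomized patients is limited to eligible, consenting patients, with the remark "Incorrectly registered patients are not included". Section 6.4 names the primary analysis population as "All randomized participants", and section 7.5 uses ITT for the primary analysis.

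**Subgroups 3 and 4.** Section 6.4 (items IV and V), the derived variables and the list that opens the output-shell tables each define these subgroups. The three versions of subgroup 3 differ; they are set side by side in the working.

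**The concern.** A SAP should let two programmers, working separately, build the same sets. Here they could differ in two places.

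First, they could disagree on whether emphysema belongs to the COPD subgroup, and one reading puts the same patients in both the COPD and the non-COPD results. Those two results would then not be independent, and neither would describe the population on its label.

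Second, they could disagree on whether a patient found after randomization to be ineligible, but who started LTOT, is in ITT. ITT is the primary analysis set, so this concerns who is in the headline result.

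Both questions can be settled from baseline and treatment-start data. As section 6 stands, they would be settled after the analyst has seen the allocation, in a trial where patients and treating staff are unblinded and the protection lies with the analyst, the UCR staff and the coordinating investigator.

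**Working it through.** **1. Which sets need allocation**

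| Set | Information used | Allocation needed? |
|---|---|---|
| ITT (3, 6.1, derived variables) | randomized, LTOT started | no |
| Safety (3, 6.3) | randomized, LTOT started | no, for membership |
| Subgroups 1 and 2 (6.4) | baseline PaO2 on air | no |
| Subgroups 3 and 4 (6.4) | primary diagnosis, spirometry | no |
| PP (6.2) | under 20 h/day in the 24 h arm; under 13 or over 17 h/day in the 15 h arm | yes |

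One qualification: recognizing a patient who started the wrong treatment, as section 6.3 mentions, does require allocation. Membership of the safety set as defined does not.

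**2. Subgroup 3 in three places**

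| Place | Diagnosis condition | Ratio condition |
|---|---|---|
| Section 6.4, item IV | COPD | below 0.7 |
| Derived variables | COPD or emphysema | below 0.7 |
| Output shells, subgroup list | none stated | below 0.7 |

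Subgroup 4 is any primary diagnosis other than COPD, both in 6.4 and in the derived variables. The derived variables code COPD as J44, and Table 6.1 lists emphysema as a primary-diagnosis category separate from COPD. Take a patient with primary diagnosis emphysema and a ratio below 0.7:

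- Section 6.4: subgroup 4 only.
- Derived variables: subgroups 3 and 4.
- Output shells, read literally: subgroups 3 and 4, as for any other non-COPD diagnosis with a ratio below 0.7.

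**3. ITT against safety**

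Under section 3 and section 6.1 the two sets have the same conditions and must be identical. Section 6.3 makes their equality conditional on there being no incorrectly randomized or wrong-treatment patients. The wrong-treatment clause could refer to the arm in which a patient is counted. The incorrectly-randomized clause has a purpose only if such a patient can be in safety but outside ITT. The eligibility-limited definitions in section 3 support that reading; section 6.1 contradicts it. Section 7.1 defines correct randomization separately, so the plan foresees such patients.

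**4. Scale for ITT**

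Inputs from section 9: margin 0.67 (coded as 1.5), one-sided alpha 0.05, power 80%, event rate 80%, 230 patients, 1:1.

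The plan's own figure first: n = (1.645 + 0.842)² / [(ln 1.5)² × 0.25 × 0.8] = 188.03, rounded up to 189. This reproduces the stated Cox sample size.

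For n patients at a true HR of 1: SE(log HR) = 2/√(0.8n), and power = Φ(−ln 0.67/SE − 1.645). The number of patients in question is an assumption.

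| In question | n | Events | SE | Power |
|---|---|---|---|---|
| 0 | 230 | 184.0 | 0.1474 | 85.8% |
| 2 (0.9%) | 228 | 182.4 | 0.1481 | 85.5% |
| 5 (2.2%) | 225 | 180.0 | 0.1491 | 85.1% |
| 10 (4.3%) | 220 | 176.0 | 0.1508 | 84.4% |

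Removing patients without regard to outcome does not shift the HR on average.

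**5. Scale for the subgroups**

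Both the number of emphysema patients with a ratio below 0.7 and the subgroup sizes are assumptions. Each pair of sizes totals 220 of 230, because COPD patients without a qualifying ratio belong to neither subgroup. Share = overlapping patients / subgroup size.

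| Sizes 3/4 | 2 patients | 5 patients | 10 patients |
|---|---|---|---|
| 160/60 | 1.2% / 3.3% | 3.1% / 8.3% | 6.2% / 16.7% |
| 140/80 | 1.4% / 2.5% | 3.6% / 6.2% | 7.1% / 12.5% |
| 115/105 | 1.7% / 1.9% | 4.3% / 4.8% | 8.7% / 9.5% |

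**The case against.** The best defence is that the rules are largely mechanical and stand in a plan that, by its own opening statement, is completed before unblinding. Whether LTOT was started, an hours cut-off, a PaO2 value and a registry diagnosis leave little to judgement, so running the classification late need not do harm. Section 6.1 says that never starting LTOT is the only ground for leaving ITT; it is the operative rule, and sections 6.3 and 3 contradict it only by implication or through general definitions. Incorrectly registered is also not the same term as incorrectly randomized. For the subgroups, COPD in subgroup 4 might have been meant to take in emphysema, since subgroup 3 beside it groups the two, and the output-shell wording may be shorthand.

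Much of this stands. A reader might infer that classifying patients after unblinding biases the primary hazard ratio or lets the analyst shape it. The documents do not support that: the room for choice is small, no affected patient is identified, and no bias can be derived from the text. Nor is the analyst the only blinded party; section 5.5 also blinds the coordinating investigator and UCR study staff. The COPD-versus-ILD wording in section 8.1 is a parenthesis in a description of data sources, not another subgroup definition.

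What does not fall away is the text itself. Subgroup 3 has different diagnosis conditions in different places, Table 6.1 separates emphysema from COPD, and section 3 attaches eligibility to the term on which section 6.1 depends. A likely intention is not a definition.

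**Conclusion.** The point holds as a consistency correction with a sensible change of order attached. Subgroup 3 is not uniquely defined, and as written in the derived variables it overlaps subgroup 4. The ITT status of an incorrectly randomized patient who started LTOT is clear in section 6.1 and clouded by sections 3 and 6.3 and the Table 1 footnote. Section 6 delays assignment of sets that do not depend on allocation.

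The size is modest. The number of patients involved is not stated and may be zero. The subgroup problem has no effect on the primary result; for an assumed 2 to 10 overlapping patients it would concern about 1 to 9% of subgroup 3 and 2 to 17% of subgroup 4. For ITT, an assumed 0 to 10 patients would move power from 85.8% to no lower than 84.4%, still above the planned 80%. These ranges rest on assumed counts, assumed subgroup sizes and the plan's 80% event rate. The contradictions follow from the text alone.

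**What to change.** - **Subgroups.** Use one definition of subgroup 3 in section 6.4, the derived variables and the output shells, and make subgroup 4 disjoint from it. If emphysema is included in subgroup 3, exclude it from subgroup 4. Say that patients with the relevant diagnosis but no qualifying ratio are in neither.
- **ITT.** Keep section 6.1. Align section 3, section 6.3 and the Table 1 footnote with it by stating that incorrectly randomized patients who started LTOT remain in ITT, analysed as randomized.
- **Order.** Amend section 6 so that ITT, safety and subgroup flags are derived and signed off before allocation is released. Lock the PP code before unblinding and run it afterwards.
- **Clerical, at the same time.** Section 6 should point to 6.4, not 6.3, for the subpopulations. Table 12 should name the safety population, to which section 6.3 assigns adverse events. The diagnosis grouping in section 8.1 should match 6.4.

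The cost is SAP wording and the sequence of programming steps. It needs no new data, no change to the rule in 6.1 and no further unblinded staff.

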6.1 Intention to treat (ITT) population

A randomized patient will only be excluded from the analysis ITT set if LTOT was never started.

6.2 Per protocol (PP) population

A randomized patient will be excluded from the PP set if LTOT has been discontinued or the mean LTOT utilization during follow-up to the primary endpoint is below 20 h/day for the 24 h/day group, and below 13 h/day or above 17 h/day in the LTOT 15 h/day group. Self-reported oxygen utilization at 12 months, or if that is unavailable, at 3 months will be used for PP classification.

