7.5 Analysis of primary variable

The primary endpoint of the composite event of death or 1st hospitalization at 1 year (day 365; day 0 being the day of randomization) is analyzed with Cox's proportional hazards model. Proportional hazard assumption will be investigated using graphical diagnostics based on the Schoenfeld residuals. The results will be presented as the hazard ratio (HR) for LTOT 24h/day vs. 15h/day with 90% two-sided

confidence interval and the one-sided p-value for the hypothesis test if the lower limit exceeds 0.67 (see section 9.1) A two-sided p-value for the difference between treatments will also be presented. (OS table 10 and table 11). The ITT population will be used for primary analysis but all endpoints will be analyzed according to both the ITT and the Per Protocol (PP) principle.

Statistical significance is defined as a p-value < 0.05. As a sensitivity analysis, the primary analysis is repeated adjusting for sex and age at randomization in years. A frailty model will be performed with “center” as a random effect to account for the clustering by hospital.

Cases withdrawing from LTOT treatment are for the primary analysis handled as

- 1) Per protocol, if it is due to improved oxygenation.
- 2) Having reached endpoint, if it is due to adverse event (such as excessive nose bleeding etc.).
- 3) Censored, if it is due to cancellation of treatment for reasons other than treatment allocation or adverse events (such as starting to smoke etc.).

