*Socialstyrelsen will provide us with the date of event. Time to event (in days) will be calculated by UCR

*Time to composite event (All-cause mortality/ All-cause Hospitalization)	Included in the order from Socialstyrelsen
*Time to all-cause mortality	Included in the order from Socialstyrelsen
*Time to 1st hospitalization	Included in the order from Socialstyrelsen
Mortality from respiratory disease	respiratory disease or infection (A40; J00-J99)
Mortality from cardiovascular disease	Underlying cause of death (UCD) heart disease (I00-I99)
Hospitalization from respiratory disease	UCD respiratory disease or infection (A40; J00-J99)
Hospitalization from cardiovascular disease	UCD heart disease (I00-I99)
Time to Mortality from respiratory disease	Death (from respiratory disease) date – Study start date
Time to Mortality from cardiovascular disease	Death (from cardiovascular disease) date – Study start date
Time to Hospitalization from respiratory disease	Date of hospitalization from respiratory disease – Study start date
Time to Hospitalization from cardiovascular disease	Date of hospitalization from cardiovascular disease – Study start date
Time from start until the patient stops being treated	End of treatment – Date for start of treatment
Discontinued LTOT	From Swedevox Registry
Withdrawals	DATE_OF_LTOT_WITHDRAWAL REASON_W
ITT	All randomized patients that start LTOT
PP	A randomized patient will be excluded from the PP set if LTOT has been discontinued before the primary outcome assessment or the mean LTOT utilization during follow-up to the primary endpoint is below 20 h/day for the 24 h/day group, and below 13 h/day or above 17 h/day in the LTOT 15 h/day group
COPD	J44; exacerbation: J44.0 and J44.1
Heart disease	I00-I99
Respiratory disease or infection	A40; J00-J99
fev1/fvc	FEV1/FVC
BMI	WEIGHT(kg)/(HEIGHT (m)*HEIGHT (m))
Age	Round down (RANDOMIZATION_DATE - DATE_OF_BIRTH)/365.25
Duration of treatment	Number of days with treatment during the study
Self-rated hours of oxygen	Self-reported oxygen use (mean hours/24h) is categorized using 1) average use since starting LTOT, or (if missing) mean h/day last week; using the

	questionnaire at 12 months, or (if missing) 3 months (and the described algorithm used for each time point).
Subgroup 1 Participants with more severe resting hypoxemia at LTOT start	PaO ₂ < 7.4 kPa breathing air
Subgroup 2 Participants with more moderate hypoxemia at LTOT start	PaO ₂ 7.4–8.0 kPa breathing air

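### The SAP does not settle whether patients who stop LTOT because oxygenation improved are in the per-protocol set, nor up to what date stopping excludes a patient, so on-treatment events can be lost.

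*SAP*

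**What the plan says.** **Membership.** Section 6.2: "A randomized patient will be excluded from the PP set if LTOT has been discontinued or the mean LTOT utilization during follow-up to the primary" (hours limits for each arm follow). No reason for stopping is exempt. The phrase about follow-up to the primary endpoint qualifies mean utilization, not discontinuation. The PP row of the derived-variable table gives the rule as "A randomized patient will be excluded from the PP set if LTOT has been discontinued before the primary outcome assessment", again with no exempt reason.

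**Withdrawals.** Section 7.5 lists how patients who withdraw from LTOT are handled, and scopes the list to the primary analysis:
- item 1: "Per protocol, if it is due to improved oxygenation"
- item 2: "Having reached endpoint, if it is due to adverse event"
- item 3: "Censored, if it is due to cancellation of treatment for reasons other than treatment allocation or adverse events"

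The same section makes ITT the primary population and requires both ITT and PP for all endpoints.

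**Timing.** Section 5.4.2: "Endpoints are assessed at 3 and 12 months after randomization (study end"). Section 5.6 places the primary endpoint at study end, one year after randomization. For hours of use, section 6.2 says "Self-reported oxygen utilization at 12 months, or if that is unavailable, at 3 months will be used for PP classification". Section 7.7 bars forms submitted after hospitalization from the primary outcome analysis. No matching rule covers discontinuation.

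**Role of PP.** Section 6 requires PP alongside ITT because non-adherence pulls the arms together and ITT is then not conservative. It also places the classification into populations after allocation is unblinded to the analyst.

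**The concern.** Two questions that decide who is in the PP set have no single answer in the SAP.

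1. Is a patient who stops because oxygenation improved in or out? Section 6.2 and the derived-variable table say out. Section 7.5 item 1 uses the SAP's own defined term and can be read as in. Nothing says which passage prevails.
2. Up to what date does stopping count? Section 6.2 gives none. The table gives one that can mean month 12 or the patient's own event. Under the month-12 reading, a patient who used oxygen as allocated, was hospitalized on day 40 and stopped on day 200 leaves PP with a valid on-treatment event.

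At stake is the reproducibility and the event count of the analysis meant to guard against a falsely reassuring ITT result. Because sets are assigned after unblinding, an open rule would be settled with allocation known.

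**Working it through.** **The plan's own figure.** Section 9.2: one-sided alpha 0.05, power 80%, null HR 1.5 (the inverse of about 0.67), event rate 80%, 1:1 allocation.
- Events: (1.645 + 0.842)² / (0.25 × ln(1.5)²) = 150.4, so 151.
- Patients: 150.43 / 0.8 = 188.03, so 189. This reproduces.
- Allowance for PP loss: 230 − 189 = 41; 41/230 = 17.8%.

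**Events lost under the month-12 reading.** The SAP gives no stopping rate, so the annual rate s is an assumption, varied from 5% to 30%. The model has exponential event times and independent exponential stopping that continues after the event, with time in years.
- Event hazard h = −ln(0.2) = 1.609; stopping hazard m = −ln(1 − s).
- Share with an on-treatment event: h/(h + m) × (1 − exp(−(h + m))).
- Share with an event left in PP if any stop within the year excludes: (1 − exp(−h)) × (1 − s).
- Power with d events: Φ(√(0.25 d) × ln 1.5 − 1.645).

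For s = 10%, m = 0.105. On-treatment: 230 × (1.609/1.715) × (1 − 0.180) = 177. Kept: 230 × 0.8 × 0.9 = 165.6. Lost: about 11.

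| Annual stopping (assumed) | On-treatment events | Kept in PP | Lost | Power, on-treatment | Power, kept |
|---|---|---|---|---|---|
| 5% | 181 | 175 | 6 | 0.86 | 0.85 |
| 10% | 177 | 166 | 11 | 0.85 | 0.83 |
| 20% | 170 | 147 | 23 | 0.84 | 0.79 |
| 30% | 162 | 129 | 33 | 0.83 | 0.74 |

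The table takes a true HR of 1 and 230 patients, before exclusions for hours of use. At 20% stopping, kept events fall below 151.

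At a true HR of 0.67 the 24 h hazard is 1.609 × 0.67 = 1.078. With s = 10%, on-treatment events are 88.5 + 72.7 = 161 (115 patients per arm), and kept events are 115 × 0.9 × (0.800 + 0.660) = 151. About 10 are lost (6%).

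The model lets every patient with an event stop afterwards. Patients whose event is death cannot, so the losses are upper-side illustrations.

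**Effect on the HR.** Same model, true HR 0.67, Cox HR from large simulated samples:

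| Stopping, 24 h / 15 h (assumed) | Exclude any stop by day 365 | Exclude stops before own event | Keep and censor at stop |
|---|---|---|---|
| 15% / 5% | 0.67 | 0.70 | 0.67 |
| 5% / 15% | 0.67 | 0.65 | 0.67 |
| 30% / 10% | 0.67 | 0.75 | 0.67 |
| 10% / 30% | 0.67 | 0.62 | 0.67 |

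When stopping is unrelated to outcome, the month-12 rule costs events but does not move the HR. Limiting the exclusion to stops before the patient's own event does move it: patients with early events have little time to stop and are retained, while patients who stay event-free for long are removed.

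**Improvement withdrawals.** Assume improvers have 0.4 times the hazard and the true HR is 0.67 within improver strata. With 5% improvers at 24 h and 15% at 15 h, the PP HR is 0.74 if they are kept and 0.67 if dropped. With the rates reversed it is 0.62 against 0.67. With 10% in both arms the gap is about 0.01. None of these inputs comes from the SAP.

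**The case against.** **The section 7.5 list is not about PP membership.** It is scoped to the primary analysis, and items 2 and 3 are coding rules for time-to-event data. Item 1 may mean only that follow-up continues as planned. This largely stands, so a reader who infers a flat contradiction between 6.2 and 7.5 goes further than the text. What remains is that the item uses a defined term, in a section that runs both ITT and PP, with no statement of precedence.

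**The timing is ambiguous, not plainly month 12.** The utilization rule runs to the primary endpoint, and section 7.7 discards forms submitted after hospitalization; both hint at an own-event limit. This also stands in part. If an own-event limit was meant, section 6.2 omits it and the table does not say it; if month 12 was meant, on-treatment events are lost. The wording needs repair either way.

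**The PP HR is therefore biased.** A reader might infer this, since dropping 15% against 5% of patients with an event moves 0.67 to about 0.62, and the reverse to 0.70. That removes only patients with events. The written rule also removes event-free patients who stop, and under independent stopping the HR then stays at 0.67. The SAP gives nothing to show that stopping depends on outcome, or in which arm.

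**ITT is primary.** Correct: PP membership does not change the primary result, which limits the consequence.

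**Conclusion.** The point holds as a defect of definition. Sections 6.2, 7.5 and the derived-variable table do not give one rule for improvement withdrawals or one date limit for discontinuation, and they must be reconciled. The demonstrable cost is PP events and power: about 10 of 161 on-treatment events at 10% annual stopping and a true HR of 0.67, and roughly 6 to 33 events over assumed rates of 5% to 30% at a true HR of 1. The choice for improvers can move the PP HR by about 0.05 to 0.07 under a threefold difference between arms and a much lower hazard in improvers, and by about 0.01 with equal rates; these are illustrations. Bias from the date limit needs stopping to be related to outcome, and its direction cannot be read from the SAP. Confidence is moderate.

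**What to change.** 1. State in section 6.2, section 7.5 and the derived-variable table one PP classification for withdrawal due to improved oxygenation, and say whether the 7.5 list applies to PP. Report the PP HR under the other classification as a sensitivity analysis.
2. Do not exclude a patient for stopping after their own event. Do not replace the rule with an exclusion cut-off at the own event either, because inclusion then depends on event time.
3. Keep patients who discontinue in the PP analysis and censor them at the LTOT withdrawal date, at least as a PP sensitivity analysis. Say how this combines with the 7.5 handling of improvement and adverse-event withdrawals.

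The cost is revised wording and one extra PP run. No new data are needed, since section 5.7 lists date and reason of LTOT withdrawal among the Swedevox items. The price is an assumption that censoring at discontinuation is non-informative, which should be stated with the result.
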